- (2) A high-quality cancer registry, which covers the entire population included in the prescription database.
- (3) A national hospital discharge registry, which covers the entire population included in the prescription database
- (4) A national death register, which can be used for record linkage to ascertain the date of death of any cohort member who died.
- (5) A source of information on key confounders (notably BMI), either in the prescription database itself, in a diabetes registry or in other available databases or large prospective studies.

The study population will include adult T2DM patients in Denmark, Norway and Sweden treated with exenatide or liraglutide (cohort 1) and these groups will be compared with patients treated with other anti-diabetics (cohort 2). Patients with previous diagnosis of the outcomes of interest will be excluded.

A unique personal identity number will be used to link together the information from the several population based registries, as shown in Figure 1:

The source of the cohorts will be mainly represented by the drug prescription registries. Patients with diabetes will be identified as having been prescribed at least one prescription for an anti-diabetic drug, i.e. ATC code 'A10' and subcategories.

High completeness of follow-up is expected, as well as high accuracy of data, which will allow capture of the variables of most interest; this is supported by our previous study (glargine and risk of cancer).

A detailed table of characteristics of the cohort included in the analysis will be provided after consultation with the local investigators.

II.9.3 Variables

The study population will include adult T2DM patients in Denmark, Norway and Sweden treated with exenatide or liraglutide (cohort 1) and these groups will be compared with patients treated with other anti-diabetics (cohort 2).

Patients with the following conditions will be excluded from the study:

1) Individuals less than 18 years of age at the cohort entry;

2) Individuals with a diagnosis of thyroid cancer, pancreatic cancer, or any pancreatitis prior to cohort entry.

Dates

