All patients who appear in the prescription registries of the countries with a record of prescription for anti-diabetes medication between the start date and end date for the centre are included in the analysis. Any patient without a record of prescription of any type of anti-diabetic medication will be excluded, as well as patients younger than 18 years at their start date. Patients with a cancer diagnosed prior to their start date (3) months after their date of first receiving anti-diabetic medication) will be excluded in the analysis as it is very unlikely that the cancer could be associated with the anti-diabetic treatment. We exclude the first 3 months from the beginning of anti-diabetes treatment because of the possibility that diabetes was caused by (or diagnosed following clinical workup for) cancer (reverse causality). As three months may be considered rather short and arbitrary length of the immortal time period to be excluded, a sensitivity analysis for exclusion of 6 months immortal time will be done. An eligible diabetes prescription is defined as only those occurring three months (or six months) or more before the censoring date (cancer, death and last date in registry). However, the three month (or six months) window will not apply for patients diagnosed with acute pancreatitis where, theoretically, this could be a rapid and acute response to an external stimulus such as therapy.

The starting date for an individual in the study is the date of first prescription of either exenatide or liraglutide for cohort 1 or the date of first prescription of other antidiabetics (e.g., oral anti-diabetics, insulins) for cohort 2 during the study period.

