The pharmacovigilance plan includes setting up a patient registry of type 2 diabetic patients taking lixisenatide. This would represent a proactive risk assessment in the post approval setting that allows for prospective follow-up and monitoring of occurrences of any of the outcomes of interest, i.e. pancreatitis, pancreatic cancer and thyroid cancer (especially medullary carcinoma of the thyroid).

The registry population will be representative of the population actually using the product since it should include all patients regardless of age, comorbidities or concurrent treatments. Follow up duration will be long enough to encompass delayed risks, consequences of long term use and effects of various combinations and alternations of treatments if any.

III.8 Research Question and Objectives

Study objectives

In the context of pharmacovigilance activity of the EU RMP (European Union Risk Management Plan), it has been agreed with the European Medicines Agency (EMA) to develop a Patient Registry of patients with diabetes exposed to lixisenatide.

The primary objectives of this study are to monitor the occurrences of:

- 1. acute pancreatitis,
- 2. pancreatic cancer
- 3. thyroid cancer, especially medullary carcinoma of the thyroid,

among adult type 2 diabetes patients treated with lixisenatide and to compare their risks with that of users of (1) other GLP-1 receptor agonists from the Database Study ; (2) other diabetic medications from the Database Study; and (3) the general population. The assembled cohort will be constantly monitored for these events to detect and emerging signal as quickly as possible.

Declaration of Study Hypotheses

This study is designed to focus on the risk associated with use of lixisenatide and will investigate the following primary hypotheses:

- 1. That adult patients prescribed lixisenatide have an increased risk of acute pancreatitis when compared to the expected risk calculated for the other GLP-1 RA users;
- That adult patients prescribed lixisenatide have an increased risk of pancreatic cancer when compared to the expected risk calculated for the other GLP-1 RA users;
- 3. That adult patients prescribed lixisenatide have an increased risk of thyroid cancer (especially medullary carcinoma of the thyroid) when compared to the expected risk calculated for the other GLP-1 RA users;

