- 3. A national hospital discharge registry, which covers the entire population included in the prescription database
- 4. A national death register, which can be used for record linkage to ascertain the date of death of any patient in the patient registry who died.
- 5. A source of information on key confounders (notably BMI), either in the prescription database itself, in a diabetes registry or in other available databases or large prospective studies.

A unique personal identity number will be used to link together the information from the several population based registries, as shown in the figure below:

The source of the cohorts will be mainly represented by the drug prescription registries.

The study population will include patients with type 2 diabetes treated with lixisenatide after launch. The study period will start from the lixisenatide launch and last for 5 years.

The patients will be identified as having been prescribed at least one prescription for the GLP-1 RA lixisenatide.

High completeness of follow-up is expected, as well as high accuracy of data, which will allow capture of the variables of most interest.

The study entry date will be defined as the date of the first prescription of lixisenatide after launch. The follow-up will end at the earliest of the following: 1) death or 2) the end of the register.

Data from national registers and databases in Denmark, Norway and Sweden will be used as the primary data source to identify lixisenatide treated patients for this registry. In Denmark, Norway and Sweden, national prescription databases have been established and are linkable to other national registers and databases (e.g., National Cancer Registry, Cause of Death Registry, and Hospital Discharge Registry) via National Registration Identification number.

A detailed table of characteristics of the cohort included in the analysis will be provided after consultation with the local investigators.

III.9.3 Variables (Outcome, Exposure, Risk factors, Confounding variables)

For each patient, information regarding all anti-diabetic medications prescribed in the study period will be recorded together with basic information such as age and gender.

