Patients who develop pancreatic cancer and thyroid cancer will be identified as well anyone who is diagnosed with pancreatitis, and their complete clinical information will be retrieved and collected from existing national registers and databases annually: smoking history, a previous diagnosis of Multiple Endocrine Neoplasia (especially MEN1), chronic pancreatitis, duration of diabetes, gallstones, prior use of other anti-diabetics, alcohol intake, obstruction of the pancreatic duct, radiation treatment to the head and neck, iodine intake, hormonal and reproductive treatment, diagnosis of Multiple Endocrine Neoplasia type 2 (MEN2), history of goitre or benign thyroid nodules, history of cancer, and family history of medullary thyroid cancer.

Outcomes of interest

Acute pancreatitis cases will be identified from the hospital discharge registers. Cases of thyroid cancer and pancreatic cancer will be identified from the national cancer registers. However, data on the cancer cases for a given year are typically considered incomplete until approximately one year after the year ends. For example, it will be possible to use the national cancer registries to identify incident cancers occurring until the end of 2013, if the analysis of thyroid cancer is planned to be performed in early 2015.

Exposure assessment and follow-up time

Patients with one or more prescriptions of lixisenatide will be identified from the national prescription registers and included in the register.

For acute pancreatitis, the exposure duration on lixisenatide will begin accumulating on the first day of lixisenatide prescription and continue with the subsequent continuous use of lixisenatide until:

- 1) the end of the lixisenatide treatment (in addition to a grace period of up to 30 days, to account for non-adherence),
- 2) the occurrence of acute pancreatitis, or;
- 3) the end of registry, whichever comes first.

For thyroid cancer and pancreatic cancer, the exposure duration will start from the first day of lixisenatide prescription and continue until either (1) the occurrence of thyroid cancer or pancreatic cancer, or (2) the end of registry, whichever comes first.

III.9.4 Data Sources

Patient registry data sources are the same as for the data base study (Section II.9.4)

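### The Registry's observed counts and the Database Study rates behind its expected counts use different lag and prior-disease rules, so the O/E ratio is not like for like

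*Protocol*

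**What the plan says.** **Expected side.** Sections III.4 (synopsis) and III.9.7 take expected numbers each year from Database Study background rates. An observed count significantly above expected may lead to further investigation after talks with regulators. The Database Study's own rules are in II.9.3:
- It excludes "Individuals with a diagnosis of thyroid cancer, pancreatic cancer, or any pancreatitis prior to cohort entry".
- For cancers it gives a 3-month window, with 6 months as a sensitivity analysis: "We exclude the first 3 months from the beginning of anti-diabetes treatment because of the possibility that diabetes was caused by" cancer, or that diabetes came to light during a cancer work-up. A prescription counts only if it precedes censoring by at least that long, and follow-up starts at drug start or three months later.
- The window is waived for acute pancreatitis.

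**Observed side.** The Registry's rules are in III.7, III.9.2 and III.9.3:
- "The study population will include patients with type 2 diabetes treated with lixisenatide after launch". One prescription is enough, and no prior-disease exclusion is listed. The stated intent is that "it should include all patients regardless of age, comorbidities or concurrent treatments".
- For cancers: "For thyroid cancer and pancreatic cancer, the exposure duration will start from the first day of lixisenatide prescription".
- For acute pancreatitis: "the exposure duration on lixisenatide will begin accumulating on the first day of lixisenatide prescription".

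Section III.8 discusses comparability (treatment mix, the general population, different calendar periods) but mentions neither the lag nor the exclusions.

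**The concern.** An O/E ratio is interpretable only if a case that can enter the numerator could also have entered the rate behind the denominator. Two kinds of case fail that test here:

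- acute pancreatitis in a patient with earlier pancreatitis;
- a pancreatic or thyroid cancer diagnosed in the first 3 months of lixisenatide.

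Both can be observed in the Registry, while the Database rates are built to leave them out. Detecting a signal is the Registry's purpose and the comparison of observed with expected is its decision rule, so a mismatch in counting rules can move the ratio with no drug effect at all. Both sets of rules are fixed in this protocol and conflict. This is not detail left for a later analysis plan.

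**Working it through.** **1. Reproduce the plan's figures (III.9.5, 1% exposure).**
- Person-years = 5 × 0.01 × 1,049,810 + 10 × 0.01 × 55,000 = 52,490.5 + 5,500 = 57,990.5, as stated.
- Expected pancreatic cancer = 57,990.5 × 29.19/100,000 = 16.9, as stated.
- Expected pancreatitis = 57,990.5 × 65.57/100,000 = 38.0, as stated.

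These planning rates stand in for the Database rates that will be used later.

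**2. Share of person-time affected by the lag.**
- Starters = 10,498.1 in year 1 + 4 × 550 later = 12,698.
- First 3 months = 12,698 × 0.25 = 3,175 person-years.
- Share s = 3,175 / 57,990.5 = 5.5%. With a 6-month lag it is 6,349 person-years, or 10.9%.

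**3. Lag mismatch alone, pancreatic cancer, no drug effect.** Let r be the rate in the first 3 months of lixisenatide divided by the later rate. Then O/E = 1 + s(r − 1). The documents give no r, so these values are assumptions. The protocol does not state whether its 0.05 level is one- or two-sided. The last column uses an exact one-sided Poisson test, which signals at 25 or more cases when 16.9 are expected.

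| Assumed r | Null O/E | Chance of a false signal |
|---|---|---|
| 1 | 1.00 | 0.039 |
| 2 | 1.05 | 0.064 |
| 3 | 1.11 | 0.097 |
| 5 | 1.22 | 0.194 |
| 10 | 1.49 | 0.548 |

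With no early excess the lag mismatch adds nothing.

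**4. Prior-disease mismatch alone, pancreatitis, no drug effect.** Let q be the share of Registry person-time from users with earlier pancreatitis, and R their rate ratio. Then O/E = 1 + q(R − 1). Both are assumptions. At 65.57 per 100,000 a year, accumulating q = 0.5% takes 0.005 / 0.0006557 = 7.6 years and q = 2% takes 30.5 years, so 0.5% to 2% is used as the range. The signal threshold is 49 or more cases when 38.0 are expected (nominal chance 0.049).

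| Assumed q | Assumed R | Null O/E | Chance of a false signal |
|---|---|---|---|
| 0.5% | 5 | 1.02 | 0.063 |
| 1% | 10 | 1.09 | 0.137 |
| 2% | 20 | 1.38 | 0.703 |

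**5. Which mismatch touches which outcome.**
- The lag concerns the two cancers only. For pancreatitis both studies count from the first day.
- The exclusion matters mainly for pancreatitis, which is found in discharge records with no first-ever restriction. For cancers, III.9.3 speaks of new cases: "it will be possible to use the national cancer registries to identify incident cancers occurring until the end of 2013" is its example. A patient with an already registered cancer mostly adds person-time without an event.

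**6. Differences that pull the other way.**
- II.9.3 seeks Database pancreatic cancers in both cancer and discharge registers, because 44% of Swedish cases were in the discharge register only. III.9.3 names cancer registers alone for the Registry, although III.9.4 links both. If III.9.3 governs and that Swedish figure applied throughout, observed counts would fall to 1 − 0.44 = 0.56 of the total. Even the largest lag effect in step 3 would then give 0.56 × 1.49 = 0.83.
- III.9.6 has Registry pancreatitis adjudicated by a committee. Section II describes no such step, so observed counts may again fall.

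**The case against.** **The window's stated reason concerns the onset of diabetes.** II.9.3 words it for the start of anti-diabetic treatment, and most lixisenatide starters will already be treated, since II.9.3 expects very few treatment-naive new users. For many of them that window has passed before lixisenatide begins. This stands in part. A reader might infer that the protocol itself labels cancers in the first 3 months of lixisenatide as reverse causality, and it does not say that. However, the lag on eligible prescriptions and the follow-up start three months later carry a window to each study drug, so the two sides still differ.

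**The net direction is not shown.** A reader might infer that the Registry's O/E will be inflated overall, for all three outcomes. The documents do not support that. Recurrence is essentially a pancreatitis argument, the lag is a cancer argument that needs an early excess, and the ascertainment and adjudication differences in step 6 can lower O/E.

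**Inclusion of all users is deliberate.** III.7 wants the Registry to represent actual users, and removing patients would undo that. This stands, and it is why any restriction should be confined to the O/E analysis.

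**The consequences are softened.** An excess only opens further investigation, prior disease is recorded for cases, and Registry methods are to be refined before the full start. This lowers the harm but does not remove the conflict. Recording prior disease among cases alone cannot correct an expected rate built without such patients.

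**Conclusion.** The mismatch is real and unreconciled. Considered separately, the prior-disease difference biases the pancreatitis O/E upward, and the lag difference biases the pancreatic cancer O/E upward if diagnoses are more frequent soon after lixisenatide is started. The only size the documents fix is the exposed share, 5.5% of cancer person-time at 1% exposure. The O/E values and false-signal chances above rest on assumed rate ratios and prevalences. They show how sensitive the rule is and are not forecasts. Overall inflation should not be claimed, because other differences between the two studies act in the opposite direction. Possible opposing errors are no reason to leave this one, since nothing makes them cancel. This reading rests on Section III; some appendix pages are absent from the copy at hand.

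**What to change.** State in III.9.3 and III.9.7 that the O/E analysis uses the same rules for observed and expected counts, and choose one of two routes:

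1. Apply the Database Study's prior-disease exclusions to the Registry's O/E analysis set. Start cancer person-time and case counting 3 months after first lixisenatide, with 6 months as a sensitivity analysis and no lag for acute pancreatitis.
2. Derive expected rates from the Database Study without the lag and without the exclusions, for use in the O/E only. Both studies retrieve and link all anti-diabetic drug users, so the data should allow it.

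Under either route, keep every lixisenatide user in the Registry and describe early cases and prior-disease cases separately. Route 1 costs about 5.5% of cancer person-time at 1% exposure (3,175 of 57,990 person-years), plus the pancreatitis events and person-time of users with prior disease. Route 2 costs an extra set of rates from each country. Both need only a few lines of protocol text and code.

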A new user approach will be favoured in order to reduce prevalent user bias and confounding from covariates that could be associated with drug use (Ray, 2003). New users are defined as patients who initiated **either GLP-1 treatment or other antidiabetic drugs** at least 6 months after the start date of the study (this will include patients who are treatment naive in regards to any anti-diabetic medication although this group will be very few in numbers). The 6 months 'criterion' was defined in previous work on these databases (Boyle et al, 2013). Figure II.9.3.1 shows possible patient trajectories; incident users (with no history of anti-diabetic treatment) are patients 5, 6 and 7 on this diagram. As all prescription databases were set up relatively recently (i.e. 2004-2005), and we will have many patients in the cohort that developed diabetes long before that, the new user approach will deal with patients for whom we have complete data on the history of anti-diabetic medication.

The period of follow-up begins at that time or three months later until a specified event takes place, either (1) date of cancer/or acute pancreatitis diagnosis; (2) date of death (right censoring, only if death occurred before the last date of available data in registry); and, (3) last date of available data in cancer registry.

Figure II.9.3.1: possible patient trajectories

Acute pancreatitis cases will be identified from the hospital discharge registers. The diagnosis of acute pancreatitis is a clinical diagnosis that hinges on the presence of abdominal pain and elevation of two biomarkers, themselves not diagnostic. One potential issue to be faced is that abdominal pain can be an unwanted side effect of the use of GLP-1 medication and this could lead to diagnostic bias.

Cases of all thyroid cancers (especially medullary thyroid cancer) and pancreatic cancer will be identified from the national cancer registers. However, data on the cancer cases for a given year are typically considered incomplete until approximately one year after the year ends. Therefore, it will be possible to use the national cancer registries in these three countries to identify incident cancers occurring until the end of 2012, if the analysis of thyroid cancer is planned to be performed in early 2014.

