For data analysis, a two stage process will be adopted because it is not possible to share individual level data. In each country an individual level analysis will be carried out using a common statistical methodology. The anonymous results (statistical model coefficients) will be transferred to the coordinating center IPRI in a secured way (password protected). Pooling of the within study effects in a meta-analysis (Thompson et al, 2010), will then be carried out at I-PRI. This same procedure was used successfully in the earlier study. Notably, no identifiable data will be made available outside the country where the data are obtained.

II.9.7 Statistical Analysis

Full details of the statistical analysis will be determined prior to the end of the period of data collection and discussed and approved by the Biostatistics Advisory Committee. This is in a similar manner to the approach adopted in the *Northern European Database Study of Glargine and Cancer* (Boyle et al, 2013). The philosophical approach to the statistical analysis will be in the spirit of this previous study, whose statistical analysis plan is attached as Appendix III.

1. Incidence rates and 95% confidence intervals (CI) of pancreatitis, pancreatic cancer and thyroid cancer among the patients treated with GLP-1 RAs as well as those patients treated with other anti-diabetic medications will be derived. In addition, fitting a Poisson regression model may be considered.

2. Hazard ratios (95% CIs) of pancreatitis, pancreatic cancer and thyroid cancer associated with the treatment of GLP-1 RAs versus other anti-diabetics will be estimated using time-dependent Cox proportional hazards survival analysis. The potential confounding factors listed above will be adjusted for in the analyses (to be further discussed and refined by external experts).

The two types of analyses above (intent-to-treat analysis and an analysis by censoring the follow up time at the end of treatment of either GLP-1 RAs or other anti-diabetics) will be stratified by age, sex, previous anti-diabetic treatments (such as insulin, metformin etc) and other confounding factors in function of their availability.

3. Profile of GLP-1 users as compared to users of other anti-diabetics, for instance: age, sex, previous prescriptions, further covariates when available.

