Data analysis Descriptive analysis will be performed and total follow-up time for lixisenatide users will be calculated. For pancreatitis, pancreatic cancer and thyroid cancer, the expected number of cases will be estimated annually after launch using the background rates obtained from the retrospective databases study. If the observed number of cases for the events of interest, respectively, is significantly higher than the expected number of cases, further investigation may be warranted following discussion with the regulatory authorities.

Milestones The registry will be initiated after the launch of lixisenatide and preparations will begin with immediate effect to ensure that the systems are in place prior to launch. Status reports will be submitted to the Agency annually, together with the RMP update as planned. Final report will be submitted to the Agency at the end of the registry.

III.5 Amendments and Updates

This is the initial protocol and any amendments will be placed here in a timely manner.

III.6 Milestones (events in months)

The registry will be initiated after the launch of lixisenatide and preparations will begin with immediate effect to ensure that the systems are in place prior to launch. Status reports will be submitted to the Agency annually, together with the RMP update as planned. Final report will be submitted to the Agency at the end of the registry.

However, if a sufficient number of participants are captured for any outcome(s) of interest earlier before the end of registry, the final data analysis for the particular outcome(s) will be started immediately and the study report will be made available within 12 months.

Start of preparatory	Т0	Development of draft Protocol	
phase	T0+1	Meeting with Sanofi Global Pharmacovigilan	
		and Epidemiology, Regulatory, and Medical	
		Affairs	
	T0+1	Establishment of Scientific and Steering	
		Committee	
	T0+2	Meeting of local Principal Investigators to refine protocol	
	T0+3	Protocol agreed and submitted to CHMP EMA	
	T0+6	Development of data collection module	
	T0+7	Synthesis of background information on	
		disease rates in populations	
	T0+8	Preliminary Pilot Testing of data collection and	
		data transfer	
	T0+9	Final agreement on Protocol from CHMP	
	T0+9	IRB/Ethics Approval	
	T0+10	Registry ready to launch	
Start of data collection	Date of mark	ket authorization for Lixisenatide – T	
End of data collection	2018		
Study progress reports	Yearly		
Interim reports	Yearly		

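### The Registry's cancer observed/expected ratio starts on the first lixisenatide day, but its expected rates come from a Database Study with a 3-month cancer window

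*Protocol*

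**What the plan says.** **Registry.** Section III.9.3 states: "For thyroid cancer and pancreatic cancer, the exposure duration will start from the first day of lixisenatide prescription and continue until either" the cancer occurs or the registry ends. III.9.2 sets study entry at the first lixisenatide prescription. No cancer lag appears in the Registry part.

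**Expected counts.** III.9.7 and the Registry synopsis take expected cases each year from the Database Study background rates. "If the observed number of cases for the events of interest, respectively, is significantly higher than the expected number of cases", further investigation may follow after discussion with the regulators.

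**Database Study, cancer (II.9.3).** "We exclude the first 3 months from the beginning of anti-diabetes treatment because of the possibility" that the diabetes was caused by the cancer or came to light during its work-up. A 6-month exclusion is the sensitivity analysis. In addition, "An eligible diabetes prescription is defined as only those occurring three months (or six months) or more before the censoring date". Acute pancreatitis is exempt: "the three month (or six months) window will not apply for patients diagnosed with acute pancreatitis".

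**Database Study, start of follow-up (II.9.3).** "The starting date for an individual in the study is the date of first prescription of either exenatide or liraglutide for cohort 1", and "The period of follow-up begins at that time or three months later until a specified event takes place".

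**Model for the analysis (II.9.7).** "The philosophical approach to the statistical analysis will be in the spirit of this previous study", meaning the glargine study in Appendix III. That plan applies its 3-month exclusion to the start of every new insulin and moves all prescription dates by 3 months.

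**The concern.** An observed/expected ratio is interpretable only if both sides count the same part of follow-up. Here the expected side has a cancer window and the observed side has none. Cancers diagnosed in the first 3 months on lixisenatide count as observed events. On the reading supported below, a cancer diagnosed equally soon after a first exenatide or liraglutide prescription does not contribute to the GLP-1 RA rate.

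If incidence is raised in that period for reasons unrelated to the drug, the ratio rises without a drug effect. The rise is largest in the early annual reports, where the first 3 months are a large share of person-time. The Registry's comparisons of pancreatic and thyroid cancer with other GLP-1 RA users and with users of other diabetic medication (III.8) depend on this ratio. Acute pancreatitis is not affected, because neither study lags it.

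**Working it through.** **1. Where does the Database Study lag start?**

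- The exclusion wording in II.9.3 dates the window from first anti-diabetic treatment. On that wording, a previously treated patient has passed the window before starting a GLP-1 RA.
- The eligible-prescription rule covers every diabetes prescription, GLP-1 RAs included. A first GLP-1 RA prescription less than 3 months before a cancer is not eligible.
- The cohort 1 starting date is the first GLP-1 RA prescription, and follow-up begins then or 3 months later. The two options fit no lag for acute pancreatitis and a lag for cancer.
- Appendix III, followed in spirit, lags each new insulin start.

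The last three points support a lag from GLP-1 RA start. The text is not fully explicit. On the narrower wording, the mismatch remains only for patients whose first anti-diabetic drug is lixisenatide.

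**2. The plan's own figure.** Inputs from III.9.5: 1,049,810 prevalent cases, 55,000 new cases a year, 29.19 pancreatic cancers per 100,000 person-years, 1% exposure.

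- Person-years over 5 years = 5 × 0.01 × 1,049,810 + 10 × 0.01 × 55,000 = 57,990.5.
- Expected cases = 57,990.5 × 29.19/100,000 = 16.9.

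Both agree with Table III.9.5.2, so the planning also counts all time from entry.

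**3. Share of person-time in the first 3 months (protocol accrual).**

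- Year 1: 0.25.
- To the end of year 2: 0.25 × (10,498 + 550) / 21,546 = 0.128.
- To the end of year 5: entrants = 0.01 × (1,049,810 + 4 × 55,000) = 12,698; 12,698 × 0.25 = 3,175 person-years; 3,175 / 57,990.5 = 0.0547.

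**4. Ratio with no drug effect.** Let m be the rate multiplier in the first 3 months, the same for all starters. Then O/E = 1 + share × (m − 1). The values m = 2, 3 and 5 are assumptions. Signal probability uses an exact one-sided 5% Poisson test, also an assumption, since III.9.5 gives 0.05 without sidedness.

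| Pancreatic cancer, 1% exposure | Expected | Cases for a signal | O/E at m = 2, 3, 5 | Signal probability at m = 2, 3, 5 | With no excess |
|---|---|---|---|---|---|
| Year 1 | 3.06 | 7 | 1.25, 1.50, 2.00 | 0.09, 0.18, 0.41 | 0.04 |
| To year 2 | 6.29 | 12 | 1.13, 1.26, 1.51 | 0.06, 0.10, 0.25 | 0.03 |
| To year 5 | 16.93 | 25 | 1.05, 1.11, 1.22 | 0.06, 0.10, 0.19 | 0.04 |

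**5. Excess confined to newly treated patients.** Taking 10% of starters as newly treated, for illustration only, O/E = 1 + share × 0.10 × (m − 1). For m = 2 to 5 this gives 1.025 to 1.10 in year 1 and 1.005 to 1.02 over 5 years.

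**The case against.** The strongest objection concerns the reason for the lag. II.9.3 is concerned with diabetes caused by cancer, or found during its work-up, at the start of anti-diabetic treatment. It does not say that incidence rises after any new drug. A reader might infer such a general effect, but the documents do not state it. II.9.3 expects very few treatment-naive new users, and II.7 notes that liraglutide is not approved as monotherapy in Europe. Most lixisenatide starters are therefore probably already treated, and the stated reason applies to them only weakly. This objection stands, and it limits the likely size.

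Second, the exclusion wording would leave GLP-1 RA rates nearly unlagged, and Appendix III belongs to another study. This stands in part: the text is ambiguous. The eligible-prescription rule is the Database Study's own, however, and it points to a lag from GLP-1 RA start.

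Third, window alignment could be left to later detail, since the introduction and III.9.1 allow refinement. That does not dispose of the point, because III.9.3 already fixes a start that conflicts with the comparator's rule.

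Fourth, day-one counting serves prompt signal detection and the general-population comparison in III.8, where no treatment-start lag exists. This stands, and the day-one result should be kept.

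Finally, a significant excess leads only to possible further investigation, and prior treatment of cases is recorded, so early cancers could be recognised on review.

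**Conclusion.** The point holds as a mismatch of rules: Registry cancers and person-time are unlagged, while the Database Study applies a cancer window that is best read as running from GLP-1 RA start. A reader might go further and conclude that the Registry ratio is biased upward or will produce false signals. The documents do not support that. They give no early cancer rate, and without an early excess there is no bias.

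The range of 1.25 to 2.00 in year 1 and 1.05 to 1.22 over 5 years assumes a 2- to 5-fold excess in every starter and the protocol's accrual, with all first-year users starting at launch. The year-1 figures rest on about 3 expected pancreatic cancers. The early annual reports are the most exposed, and the 5-year effect is small unless the early excess is large. Priority is low to moderate.

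**What to change.** - **III.9.3 and III.9.7:** for the cancer ratio against Database Study rates, start Registry events and person-time 3 months after the first lixisenatide prescription, with 6 months as sensitivity.
- **Keep the day-one ratio** as a supplementary result and for the general-population comparison, so that no early cancer is hidden.
- **II.9.3:** state in one sentence that the cancer lag for cohort 1 runs from the first GLP-1 RA prescription.
- **Acute pancreatitis:** leave unlagged in both studies.

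The change needs no new data, only dates already held. At 1% exposure, 5-year person-time falls by 5.5%, from 57,990.5 to 54,816. Expected pancreatic cancers fall from 16.9 to 16.0, and exact one-sided power at a ratio of 2 falls from 0.952 to 0.939. With a 6-month lag the figures are 15.1 and 0.923. The protocol states 0.92 without a lag; the exact test is used here on both sides so that the difference is like for like. For thyroid cancer at 5% exposure, expected cases fall from 17.8 to 16.8 and power from 0.960 to 0.947. Year 1 loses the most: 25% of person-time, or 3.06 to 2.30 expected pancreatic cancers.
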